## 9 Sample size justification

The sample size for this study was estimated based on limited available natural history data for the target population and data from studies ISIS 396443-CS1 and ISIS 396443-CS2. Seventy patients in the treated group and 35 patients in the control group will give at least 90% power to detect a 3-point difference between control and treated groups in the change from baseline HFMSE with a standard deviation of 4.4, using a two-sided test with an alpha level of 0.05. 117 patients enrolled will ensure that a small dropout rate will not affect the power of the primary efficacy analysis.

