**10.2 Sample Size Considerations**

The sample size for this study was estimated based on limited available natural history data for the target population and data from the ISIS 396443-CS1 and ISIS 396443-CS2 clinical studies. Seventy (70) patients in the treated group and 35 patients in the control group will give at least 90% power to detect a 3-point difference between control and treated groups in change on the HFMSE with a standard deviation of 4.4, using a 2-sided t-test with an alpha level of 0.05. The sample size was estimated using n-Query. One hundred seventeen (117) patients enrolled will ensure that a small dropout rate will not affect the power of the primary efficacy analysis.

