### 5.1 Interim and final efficacy analyses

An interim analysis may take place when all subjects have completed the 6-month assessment and at least 39 subjects have completed the 15-month assessment with a targeted clinical cut-off date of 31 August 2016. At the interim analysis, only the primary endpoint will be tested. The final efficacy analysis will take place when the last subject completes the 15-month assessment or earlier if the study is terminated on the grounds that conducting a sham-controlled study is no longer deemed ethical based on the assessment of risk-benefit of ISIS 396443.

At the interim analysis and final analysis, the same analysis of covariance (ANCOVA) model will be used in analyzing the change from baseline in HFMSE score to month 15. At the interim analysis, the month 15 endpoint values will not be available for some patients, so a multiple imputation method will be used to estimate them ([Section 5.3](#)). This method will also be used in the final analysis for the primary endpoint

The interim analysis results will be reviewed by an independent Data Safety Monitoring Board (DSMB) and an Unblinded Senior Management Team from the Sponsor. Recommendation will be made on whether it is appropriate for the trial to continue according to the current protocol or whether the protocol needs to be modified. During the interim analysis, subjects will continue in the study.

In the protocol it had been planned to conduct the interim efficacy analysis with an alpha of 0.02, however in finalizing this statistical analysis plan it was decided to conduct the interim analysis at a significance level of 0.025. If the study is not stopped at the interim analysis, the final analysis (test and confidence interval estimate procedures) will be conducted at a significance level determined by the resampling procedure as follows.

Let  $T_1$  and  $T_2$  be the standardized test statistics at the interim and final analyses, respectively. In order to determine the alpha level for the final analysis, the correlation between  $T_1$  and  $T_2$  is first estimated based on the resampling approach (Westfall and Young 1993):

- Among the 126 subjects enrolled in the study, randomly assign 84 subjects to the ISIS 396443 group and 42 subjects to the sham control group.
- Apply the re-randomized treatment assignment to the interim data and obtain the standardized test statistics  $T_1$ .

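### The 90% power stated for 70:35 patients is single-test power at 0.05; under the SAP's two-look rule the same 105 evaluable patients give about 87-90%, and neither document says so

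*SAP*

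**What the plan says.** SAP section 9 sizes the trial on 70 treated and 35 control patients, which it says "will give at least 90% power to detect a 3-point difference between control and treated groups in the change from baseline HFMSE", with an SD of 4.4, "using a two-sided test with an alpha level of 0.05". Protocol 10.2 gives the same basis: "using a 2-sided t-test with an alpha level of 0.05". Both add that enrolling 117 protects power against a small dropout rate; neither gives a rate. Neither passage mentions an interim look.

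The testing rule is in SAP 5.1 and 5.2. On the interim, "it was decided to conduct the interim analysis at a significance level of 0.025" (protocol 10.5 has 0.02). If the study continues, "the final analysis (test and confidence interval estimate procedures) will be conducted at a significance level determined by the resampling procedure as follows". The final critical value is solved so that the two looks together spend 0.05, using a correlation to be estimated later by re-randomization. If the interim is significant, the primary endpoint is not tested again. The re-randomization step begins "Among the 126 subjects enrolled in the study" and splits them 84:42.

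**The concern.** The power statement describes one test at 0.05. When the interim is done, no test of the primary endpoint is made at that level: the first is at 0.025, and the second must be below 0.05 because part of the error has been spent. The single-test margin over 90% is 0.4 points, so almost any reduction in level uses it up.

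Two pre-specified properties depend on this. One is the power attached to 105 evaluable patients. The other is the dropout cushion said to come from enrolling 117, which shrinks if 90% needs more than 105.

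**Working it through.** **Inputs.** 70:35 evaluable, difference 3, SD 4.4, two-sided 0.05 (SAP 9, protocol 10.2); interim level 0.025 and the equation for the final cut-off (SAP 5.1); about 52 of 126 patients with Month 15 data expected at the interim, and a minimum of 39 (SAP 2 and 5.1). The correlation rho between the interim and final statistics is not given and is assumed here.

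**Step 1: the plan's own figure.** Standardized drift θ = 3 / (4.4 × √(1/70 + 1/35)) = 3 / 0.911 = 3.29. Noncentral t with 103 df at two-sided 0.05 gives 90.4% (normal approximation 90.9%). The statement reproduces. The level at which power is exactly 90% is 0.0477.

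**Step 2: the final level.** With c1 = 2.241 (two-sided 0.025), solve Pr(|T1| ≥ c1 or |T2| ≥ c2) = 0.05 for a standard bivariate normal with correlation rho.

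**Step 3: overall power.** Power is the probability of rejecting at either look, with mean θ for T2 and rho × θ for T1. It was simulated with t critical values, so the last digit carries simulation error.

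| rho (assumed) | c2 | final level | 105 evaluable | 117 evaluable | 126 evaluable |
|---|---|---|---|---|---|
| 0.5 | 2.185 | 0.029 | 86.6% | 90.1% | 92.2% |
| 0.64 | 2.148 | 0.032 | 87.5% | 90.9% | 92.8% |
| 0.7 | 2.128 | 0.033 | 88.0% | 91.3% | 93.2% |
| 0.8 | 2.084 | 0.037 | 88.9% | 91.9% | 93.7% |
| 0.9 | 2.025 | 0.043 | 89.8% | 92.7% | 94.3% |
| 0.95 | 1.988 | 0.047 | 90.1% | 93.0% | 94.6% |

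On the normal scale the 105 column runs from 87.4% (rho 0.5) to 90.4% (rho 0.9), to be compared with 90.9% for the single test. With protocol 10.5's interim level of 0.02 it would run from 88.4% to 90.6%.

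**Where rho might lie.** Complete Month 15 cases alone suggest √(52/126) = 0.64, or √(39/126) = 0.56 at the minimum trigger. The interim also imputes Month 15 from earlier visits, which could raise rho. So 0.5 is a cautious lower end.

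**Step 4: numbers needed and the cushion.** For 90%, about 117 evaluable are needed at rho 0.5, 112 at 0.7 and 106 at 0.9. Counting each dropout as wholly lost, 117 enrolled leave room for 117 − 105 = 12 losses (10%) under the single test. Under the two-look rule they leave 0 at rho 0.5, 117 − 112 = 5 (4%) at 0.7 and 117 − 106 = 11 (9%) at 0.9.

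**The case against.** The strongest reply is that SAP 9 names its conditions and is true under them. That stands: there is no arithmetic error, and the sentence should not be deleted.

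Second, the interim is not uniformly definite. SAP section 2 says it will be done, but SAP 5.1, 5.5 and 5.5.2 and protocol 10.5 leave it optional. If it were dropped and the final test were made at 0.05, the stated figure would apply. That is a reason to label the figure. It does not remove the need to give power for the case section 2 expects.

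Third, rho is unknown, so no single value such as 88% can be claimed. That stands too, and is why a range is given. At the top of the range the shortfall all but disappears.

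Fourth, the planned analysis is ANCOVA with age and baseline HFMSE. If 4.4 is an unadjusted SD, covariates explaining about 6% of the variance (1 − 105/112) would restore 90% at rho 0.7. The documents give no such figure, so the gain cannot be credited. Equally, 87-90% is the power of an unadjusted t-test under the two-look rule and must be described that way.

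Fifth, no dropout rate is stated, so the 10% in Step 4 is inferred from 117 against 105. Multiple imputation also keeps dropouts' partial data, so counting each as a full loss overstates the cost.

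A reader might also infer that 117 is a mistake for 126. It is not: 117 is planned enrolment, 126 is what the SAP reports as enrolled, and protocol 3.3 caps the number at 130.

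**Conclusion.** The point holds as a sample-size statement that does not cover the testing rule in SAP 5.1-5.2. With the interim done, 105 evaluable patients give about 87-90% overall power (87.5-88% for rho 0.64-0.7), against 90.4% for the single test. This assumes a difference of 3, SD 4.4, an unadjusted t-test, interim drift equal to rho times final drift, and rho from 0.5 to 0.9. Power reaches 90% only at rho of about 0.9 or higher: by 0.9 on the normal scale, between 0.9 and 0.95 on the t scale.

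A reader might conclude that the trial is underpowered. The documents do not support that. Power stays at or above 90% with 117 evaluable patients at every rho in the table, and is about 92-94% with the 126 enrolled for rho 0.5-0.9. No error rate or decision rule is affected.

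**What to change.** In SAP 9 and protocol 10.2:

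- Keep the 90% figure for 70:35, labelled as the power of a single two-sided test at 0.05.
- Add the overall power of the two-look rule, with rho stated as an assumption and shown as a range: 70:35 evaluable gives about 87-90%; 90% needs about 106 to 117 evaluable for rho 0.9 down to 0.5; 117 evaluable gives about 90-93%; 84:42 with no loss gives about 92-94%.
- Say that any gain from the ANCOVA covariates is not counted.
- Give 126 as actual enrolment beside the planned 117, without replacing it.
- Qualify the assurance that 117 enrolled protects power from dropout, since the tolerable loss depends on rho.

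The cost is wording, plus a power figure for 105 patients that is up to about 4 points lower. It needs no added patients and no change in conduct or testing.
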